8.3 Statistical methods

Describe the statistical methods (or non-statistical methods of analysis) that will be employed.

Descriptive data will be used for demographic characteristics as well as visual and refractive outcomes. A Shapiro-Wilk test will be used to assess the normality of the data. Visual acuities will be converted to logMAR notation to facilitate averaging and analysis.

The paired sample t-test or nonparametric Wilcoxon signed-rank test will be used to compare monocular and binocular visual acuity under uncorrected and distance-corrected conditions. Comparisons between patients with different IOLs will be evaluated with independent sample t-tests or the nonparametric Mann-Whitney test for visual acuity and refractive outcomes, depending on the normality of the data. The level of significance will be set at $p < 0.05$.

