1.2 Primary Study Endpoints

State the primary endpoints to be measured in the study.

Clinical trials typically have a primary objective or endpoint. Additional objectives and endpoints are secondary. The endpoints (or outcomes), determined for each study subject, are the quantitative measurements required by the objectives. Measuring the selected endpoints is the goal of a trial (examples: response rate and survival).

Primary endpoints will include:

Mean logMAR best-distance corrected visual acuity at intermediate (66 cm) tested in binocular photopic conditions at 3 months.

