8.2 Sample size determination

If applicable, provide a justification of the sample size outlined in section 8.1 to include reflections on, or calculations of, the power of the study.

The FDA Summary of Safety and Effectiveness Data on the Alcon Vivity IOL compared the Alcon Vivity IOL to the Alcon Acrysof IQ SN60WF. It demonstrated binocular DCIVA's of 0.054 (SD = 0.09) and 0.196 (SD 0.113) logMAR units, respectively (Table 25; difference of 0.142). The difference between the DCNVAs was similar.⁸ We hypothesize that the neutral asphericity of the B&L enVista IOL will result in a slightly improved DCIVA and DCNVA as compared with that of the SN60WF. As such, we assumed that the mean difference in the DCIVA or DCNVA between the two study devices will be ≥ 0.12 logMAR units and that the standard deviation on these measurements will be approximately 0.10.^{8,11}

A 2019 ASCRS abstract by [name] also described the MX60E as having monocular UCIVA and UCNVA of 0.17 ± 0.17 and 0.44 ± 0.33 D, respectively.¹² Binocular UCIVA and UCNVA for the Alcon Vivity IOL was 0.058 ± 0.083 and 0.208 ± 0.104 D, respectively (monocular logMAR not reported).⁸ Although monocular and binocular acuities are not typically compared, the difference between the Vivity and MX60E IOLs might be approximately 0.11 for intermediate and 0.24 logMAR units, based upon this above information. The higher SDs are likely due to the uncorrected astigmatism in this population.

The sample size calculation was performed using <http://clincalc.com>. Based on a difference in binocular DCIVA of 0.12 logMAR units and a SD of 0.10, we calculated that for an α of 0.05 and power of 0.80, 22 bilaterally implanted patients would be required in each group. However, 28 patients were included to more closely approximate a normal distribution and ensure adequate numbers after accounting for screen failures and patients lost to follow-up.

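### The primary endpoint is a mean, but a normality pre-test with no stated level or data set decides whether the primary test compares means at all

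*Combined protocol and SAP*

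**What the plan says.** Section 1.2 gives one primary endpoint: "Mean logMAR best-distance corrected visual acuity at intermediate (66 cm) tested in binocular photopic conditions at 3 months". Section 8.2 builds the sample size on the same scale: "Based on a difference in binocular DCIVA of 0.12 logMAR units and a SD of 0.10".

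Section 8.3 announces the pre-test ("A Shapiro-Wilk test will be used to assess the normality of the data") and then gives the between-lens comparison as "independent sample t-tests or the nonparametric Mann-Whitney test for visual acuity and refractive outcomes, depending on the normality of the data", at a 0.05 significance level. It names no separate analysis for the primary endpoint, so this rule governs it. Section 9.7 repeats the same choice of tests.

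The plan does not state:
- the significance level of the Shapiro-Wilk test;
- whether it is run in each arm, on the pooled data or on residuals;
- a between-arm effect estimate or confidence interval, on either branch.

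**The concern.** The endpoint and the sample size concern a difference in means. The t-test addresses that quantity. Mann-Whitney addresses whether a value from one arm tends to exceed a value from the other, which is the same question only if the two distributions have the same shape and differ by a shift. Under section 8.3 the trial's own data decide which question is answered, through a trigger that is only partly specified. Two analysts could follow the section faithfully and run different primary tests.

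Two things are at stake: whether the reported p-value refers to the stated endpoint, and whether the 5% level holds for the difference in means.

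**Working it through.** **Inputs.** Difference 0.12 and SD 0.10 (section 8.2); alpha 0.05 (sections 8.2 and 8.3; two-sided assumed); 22 per group required and 28 planned (section 8.2). I read 28 as per group because 2 × 28 = 56, the enrolment in section 15.2; section 8.1 gives 70. SDs of 0.09 and 0.113 are quoted in section 8.2 for Vivity and SN60WF. Distribution shapes are my assumptions.

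**1. The plan's own figure.** The usual formula is n per group = 2(z₀.₉₇₅ + z₀.₈₀)²(SD/difference)² = 2 × (1.960 + 0.842)² × (0.10/0.12)² = 10.9, so 11 (12 with the noncentral t). The stated 22 per group is not reproduced; it equals the two-arm total, 2 × 11. That is a separate matter and does not affect this point.

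**2. Power of a single named test of means at 0.12.** Power ≈ Φ(difference/(SD√(2/n)) − 1.96).
- n = 22: 0.12/(0.10 × √(2/22)) = 3.98, and Φ(2.02) = 97.8% (noncentral t: 97.3%).
- n = 28: 0.12/(0.10 × √(2/28)) = 4.49, and Φ(2.53) = 99.4% (noncentral t: 99.3%).

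**3. Why Mann-Whitney can reject when means are equal.** Take the extreme case of an exponential shape (gamma shape 1): a fraction 1 − e⁻¹ = 63% of values lie below the mean. Against a symmetric arm with the same mean, most of the skewed arm lies lower. Mann-Whitney counts that as a difference although the means are equal.

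**4. Type I error of the two-stage rule for the mean difference.** Simulation with 28 per arm and equal means. Shapiro-Wilk at 0.05 in each arm (assumed): if either rejects, Mann-Whitney; otherwise the pooled t-test. There were 4,000 to 6,000 trials per run, so the Monte Carlo standard error near 5% is about 0.3 points. Skewed arms are shifted gammas, and ranges are across repeat runs. Acuity was rounded to 0.02 logMAR or left unrounded, except in the last row.

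| Assumed distributions | Two-stage type I error |
|---|---|
| Both normal, equal SDs or 0.09/0.113 | 5.1–5.4% |
| Both gamma shape 2, equal SDs | 4.6–5.2% |
| Both mildly skewed (shape 8), SDs 0.09/0.113 | 5.0–5.7% |
| Both gamma shape 2, SDs 0.09/0.113 | 5.9–6.9% |
| Gamma shape 2 (SD 0.09) vs normal (0.113) | 5.8–6.6% |
| Gamma shape 2 vs normal, equal SDs | 6.7% |
| Normal (0.09) vs gamma shape 2 (0.113) | 7.8–8.5% |
| Normal (0.09) vs gamma shape 1 (0.113) | 10.0–10.9% |
| Opposite skews, shape 4 | 9.1–9.5% |
| Opposite skews, shape 2 (extreme) | 13.9% |
| Both normal, scored in 0.1 logMAR steps | 4.5–5.5% |

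Welch's test stayed at about 4% to 6% throughout.

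**5. How often the switch happens.** With both arms normal, Mann-Whitney is chosen in about 10% of trials if each arm is tested and 5% if the data are pooled, so the unstated detail matters. With gamma shape 2 in both arms it is chosen in 83% of trials at 22 per arm and 92% at 28. With normal acuity scored in 0.1 steps it is chosen in over 99% at 28 per arm; with 0.02 steps, about 12%.

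**6. Does the choice change conclusions?** At a true difference of 0.12, every option had about 97% power or more at 28 per arm (at least 95% at 22). At a true difference of 0.06, the t-test and Mann-Whitney disagreed on significance in 7% to 8% of normal trials and 15% of gamma trials.

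**The case against.** The best defence is that the rule is written down in advance. Section 8.3 names the pre-test, both candidate tests and the 0.05 level, so this is not a free choice after the data are seen. That stands, except that the missing Shapiro-Wilk level and data set leave some discretion.

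A second defence is that section 1.1 frames the hypothesis as similar acuity and treats rejection as a sign that visual performance may differ. On that broad reading, a Mann-Whitney rejection when the distributions differ is not a false positive. This softens the error-rate argument but does not remove the mismatch with section 1.2, which specifies a mean.

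Third, means would still be reported: section 8.3 provides descriptive statistics and converts acuity to logMAR so that it can be averaged. True, but no between-arm difference or interval is named on either branch.

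Three stronger readings are tempting, and the documents do not support them.
- **That the 5% level is generally broken.** Rates of about 8% or more need one arm near normal and the other clearly skewed, or opposite skews. The documents give no information on shape.
- **That the quoted SDs, "0.054 (SD = 0.09) and 0.196 (SD 0.113) logMAR units", show that shapes differ.** An SD is not a shape; normal arms with those SDs give 5.1% to 5.4%. The 0.113 belongs to SN60WF, which is not a study lens.
- **That ties from coarse scoring inflate the error.** Section 7.2 specifies ETDRS testing but no scoring step. Even with 0.1 steps, where Mann-Whitney is nearly always chosen, the error stays near 5%. What changes is which test is used.

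**Conclusion.** The point holds, as a mismatch between endpoint and test. Under section 8.3 the primary test may not be a test of the mean difference that sections 1.2 and 8.2 are built on, and which test is run depends on an incompletely specified preliminary test. This follows from the text under any distribution.

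The numerical harm is conditional. Type I error for the mean difference is about 5% if the arms are normal or share shape and SD, about 6% to 7% with moderate skew and unequal SDs, and about 8% to 11% with clearly different or opposite skews (near 14% in the most extreme case tried). These figures assume Shapiro-Wilk at 0.05 in each arm, two-sided tests, 28 per arm and gamma-type skew. If the lenses differ by the planned 0.12, the choice of test will rarely change the conclusion; it matters mainly for small or null differences. This is a change worth making before analysis, not a threat to the trial's validity.

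The extra patients that section 8.2 adds partly for the sake of normality do not resolve it. A larger sample does not make acuity normal, and it makes Shapiro-Wilk more likely to reject when acuity is not.

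**What to change.** In section 8.3, name the primary analysis as the between-lens difference in mean 3-month binocular DCIVA, with a Welch t-test and 95% confidence interval, regardless of the Shapiro-Wilk result. Use Shapiro-Wilk descriptively only, and report Mann-Whitney as a sensitivity analysis. Apply the same rule to the other mean acuity endpoints in section 1.3, and align section 9.7.

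The cost is a few sentences, with no new patients, visits or data. The downside is a small loss of power if outliers are heavy, which the sensitivity analysis would reveal. At the planned difference, Welch's power remained about 97% or more at 28 per arm in the normal and skewed scenarios tried.

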3.3.2 Follow-up for withdrawn subjects

Describe when and how to withdraw subjects from the study; the type and timing of the data to be collected for withdrawal of subjects; whether and how subjects are to be replaced; the follow-up for subjects withdrawn from investigational treatment.

Subjects who fail to meet protocol eligibility criteria prior to IOL implantation will not be followed beyond the date they are determined to be ineligible. Subjects who terminate due to the occurrence of an adverse event will be followed until resolution or stabilization of the event.

Terminated subjects who have undergone IOL implantation will not be replaced.

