Table 1: Schedule of Clinical Assessments / Procedures

Assessment / Procedure	Protocol Visit							
	Pre-operative/ Visit 1	Operative #1/ Visit 2	1 Day #1/ Visit 3	1 Week / Visit 4	Operative #2/ Visit 5	1 Day #2/ Visit 6	1 Month/ Visit 7	3 Month/ Visit 8
Medical and ophthalmic history	SOC							
Slit lamp examination	SOC		SOC	SOC		SOC	SOC	SOC
Dilated fundus examination	SOC						SOC	
Intraocular pressure	SOC		SOC	SOC		SOC	SOC	SOC
Pre-operative biometry	SOC							
Macular optical-coherence tomography	SOC							
Corneal topography	SOC							
Informed consent	R							
Randomization to study arm	R							
Cataract extraction with IOL implantation		SOC			SOC			
Manifest refraction				SOC			SOC	SOC
Snellen uncorrected distance acuity	SOC		SOC	SOC		SOC	SOC	SOC
Uncorrected distance visual acuity (UDVA) monocular and binocular							R	R
Corrected distance visual acuity (CDVA) monocular and binocular							R	R
Uncorrected intermediate visual acuity (UIVA) monocular							R	R

and binocular								
Distance corrected intermediate visual acuity (DCIVA) monocular and binocular						R	R	
Uncorrected near visual acuity (UNVA) monocular and binocular						R	R	
Distance corrected near visual acuity (DCNVA) monocular and binocular						R	R	
Defocus Curve Testing (binocular only)								R
Un-blinding								R
Patient Reported Outcomes	R							R
Adverse Event Monitoring	R	R	R	R	R	R	R	R
Urine Pregnancy test	R							

SOC = standard-of-care; R = research

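### The 3-month two-sample test gives no role to the 1-month binocular DCIVA already collected, so subjects lost between the two visits contribute nothing: a small precision cost, and bias if that loss relates to acuity

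*Combined protocol and SAP*

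**What the plan says.** Section 1.2 defines the primary endpoint as "Mean logMAR best-distance corrected visual acuity at intermediate (66 cm) tested in binocular photopic conditions at 3 months". Section 8.3 gives the comparison between lenses: "Comparisons between patients with different IOLs will be evaluated with independent sample t-tests or the nonparametric Mann-Whitney test", with the choice depending on normality.

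Table 1 in section 7.2 has a research row for "Distance corrected intermediate visual acuity (DCIVA) monocular and binocular". The visit lists place this acuity testing at both the 1-month and the 3-month visit, each after the second eye has been operated on. Section 7.2 assigns both visits to the blinded investigator. No DCIVA is scheduled earlier.

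Section 3.3.1 lists loss to follow-up among the reasons for leaving the study, and section 3.3.2 adds: "Terminated subjects who have undergone IOL implantation will not be replaced". The only provision for loss is in section 8.2, which raises 22 per group to 28, partly to "ensure adequate numbers after accounting for screen failures and patients lost to follow-up". The plan names no analysis set, missing-data method, repeated-measures model or sensitivity analysis.

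**The concern.** The best available predictor of a missing 3-month DCIVA is the same subject's 1-month DCIVA. The trial collects it, but the primary comparison as described gives it no role. Two things follow.

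- **Precision.** A subject seen at 1 month and then lost carries information about the 3-month mean. A two-sample test of 3-month values cannot use it.
- **Bias.** If return at 3 months depends on acuity, those who return are a selected group. When the selection falls unequally on the two arms, the difference among completers is not the difference among those implanted. If poor acuity drives loss from the arm with poorer intermediate vision, the lens difference shrinks. Section 1.1 hypothesises that the lenses perform alike, so shrinkage would favour the stated hypothesis.

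**Working it through.** **Inputs from the plan.** Difference 0.12 logMAR, SD 0.10, alpha 0.05 (two-sided assumed), power 0.80, 22 per group required, 28 per group planned (all section 8.2). The 28 is read as per group because section 15.2 gives 56 in total.

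**Inputs assumed, because the plan gives none.** Correlation r between 1- and 3-month DCIVA: 0.5 to 0.9 for precision and the simulations, 0.5 to 0.8 for the common-rule calculation. The number lost and the dropout mechanism are also assumed.

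**1. The plan's own sample size.** n per group = 2 × 0.10² × (1.960 + 0.842)² / 0.12² = 10.9, so 11 per group (12 with the exact t distribution). The stated 22 per group is not reproduced; it equals the two-arm total. That is a separate matter, but it shows the margin here: at 22 per group power is 0.973 (t) or 0.978 (normal approximation), and at 28 it is 0.993 or 0.994.

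**2. The possible loss.** (28 − 22)/28 = 21.4%. Section 8.2 gives three reasons for the increase (approximating normality, screen failures, loss to follow-up) and does not divide it among them. So 21% is an upper bound on the loss allowed for.

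**3. Precision.** Let m be the number per arm with a 3-month value and n1 the number with a 1-month value. The variance of the 3-month arm mean is SD²/m for the t-test. For a likelihood analysis of both visits it is SD² × [(1 − r²)/m + r²/n1]. The SE of the difference is the square root of twice this variance.

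| m | n1 | t-test SE | Model SE, r = 0.5 / 0.7 / 0.9 | SE reduction |
|---|---|---|---|---|
| 22 | 28 | 0.0302 | 0.0293 / 0.0285 / 0.0274 | 2.7 / 5.4 / 9.1% |
| 22 | 25 | 0.0302 | 0.0297 / 0.0293 / 0.0286 | 1.5 / 3.0 / 5.0% |
| 26 | 28 | 0.0277 | 0.0275 / 0.0272 / 0.0269 | 0.9 / 1.8 / 2.9% |
| 26 | 27 | 0.0277 | 0.0276 / 0.0275 / 0.0273 | 0.5 / 0.9 / 1.5% |

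In the first row, power by the normal approximation rises from 0.978 to 0.984 / 0.988 / 0.992.

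**4. Bias under one acuity rule common to both arms.** Take arm means of 0.054 (the Vivity figure in section 8.2) and 0.054 + 0.12 = 0.174, with SD 0.10. Suppose any subject whose 1-month DCIVA is worse than a threshold c is lost. With a = (c − mean)/SD, an arm's 3-month completer mean falls by r × SD × φ(a)/Φ(a). The bias in the difference is the gap between the arms.

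| c | Lost, better / worse arm | φ/Φ, better / worse arm | Shrinkage, r = 0.5 to 0.8 |
|---|---|---|---|
| 0.25 | 2.5% / 22.4% | 0.060 / 0.385 | 0.016 to 0.026 |
| 0.30 | 0.7% / 10.4% | 0.019 / 0.201 | 0.009 to 0.015 |
| 0.35 | 0.2% / 3.9% | 0.005 / 0.088 | 0.004 to 0.007 |

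The full range is 0.004 to 0.026 logMAR. As a share of 0.12, this is 0.004/0.12 = 3% to 0.026/0.12 = 22%. The top of the range needs 22.4% lost in one arm, slightly above the 21% bound.

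**5. Bias with a fixed 6 of 28 lost per arm** (simulation, 3,000 trials per setting, r = 0.5 / 0.7 / 0.9).

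- Loss random, or related to 1-month acuity to the same degree in both arms: t-test bias about 0.
- Loss related to poor 1-month acuity in the worse arm only: t-test bias −0.013 / −0.018 / −0.023, t-test power 0.94 / 0.92 / 0.90. Using the 1-month value brings the bias to about 0.
- Loss in that arm related to the 3-month value itself: t-test bias −0.026 / −0.027 / −0.025. Using the 1-month value reduces it to −0.020 / −0.015 / −0.006 but does not remove it.

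**The case against.** A two-sample test is a valid analysis of a continuous endpoint at one time point, and the plan does not say that it sets 1-month data aside. That is inferred from the named tests and from silence about missing values. The precision gain is slight and power is ample. The documents do not suggest that dropout would follow acuity. Subjects stay masked to their lens until the 3-month visit, and section 13.0 pays them at both the 1-month and 3-month visits, which supports retention. All of this stands and keeps the point small.

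It can also be said that bias requires a contrived rule in which acuity drives loss in one arm only. This part does not stand. When equal numbers are lost under the same relative rule, the bias is indeed about zero. But section 8.2 assumes that the arms differ by 0.12, so a single absolute threshold removes more subjects from the worse arm and biases the difference without any arm-specific behaviour (step 4).

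Two stronger readings are tempting. A reader might infer that the plan expects about 21% to be lost. It does not: the increase to 28 also serves other stated purposes. Nor can the whole increase be assigned to loss on the ground that screen failures precede randomisation. Section 7.2 does assign the lens after eligibility is confirmed, but section 3.3.1 still allows termination for ineligibility up to the first operation. A reader might also infer that the data needed to repair any dropout are already collected. They are not: subjects lost before 1 month, or never implanted in the second eye, have no binocular DCIVA with both study lenses.

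**Conclusion.** The point holds as an optional improvement. As described, the primary comparison gives the 1-month binocular DCIVA no role, so subjects lost between 1 and 3 months contribute nothing. The precision at stake is about 0.5 to 9% of the SE, depending on how many are lost after 1 month and on the assumed correlation. Acuity-related dropout could shift the estimate by roughly 0.004 to 0.026 logMAR, which is below one SE (about 0.03) but is a systematic error that ample power does not correct.

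The documents do not support the view that the planned test is invalid or the trial underpowered. Nor would a repeated-measures model cure dropout bias in general: it does so only if loss depends on the observed 1-month acuity, and otherwise reduces it. The dropout rates, mechanisms and correlations are assumptions; only the 0.12, the SD of 0.10, the Vivity mean of 0.054 and the group sizes come from the plan.

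**What to change.** In section 8.3, make the primary analysis a likelihood-based repeated-measures model of binocular DCIVA at 1 and 3 months, with lens, visit and lens-by-visit terms and an unstructured within-subject covariance. Include all randomised, implanted subjects with at least one post-operative binocular DCIVA, in their assigned arm. Report the 3-month lens difference with its 95% confidence interval as the primary result. Keep the planned t-test or Mann-Whitney comparison as a sensitivity analysis, which also retains the nonparametric route. Report the number lost before 1 month and between 1 and 3 months, by arm, so that readers can see how far the model can help.

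The cost is a slightly more complex primary model and a little more analysis work, with no new visits, subjects or measurements. If few are lost after 1 month, the gain is small; if nobody is lost, the 3-month estimate is essentially unchanged.

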9.0 Data and Safety Monitoring Plan

This section is required when research involves more than Minimal Risk to subjects as defined in “HRP-001 SOP- Definitions.”

Minimal Risk is defined as the probability and magnitude of harm or discomfort anticipated in the research that are not greater in and of themselves than those ordinarily encountered in daily life or during the performance of routine physical or psychological examinations or tests. For research involving prisoners, Minimal Risk is the probability and magnitude of physical or psychological harm that is normally encountered in the daily lives, or in the routine medical, dental, or psychological examination of healthy persons.

Please complete the sections below if the research involves more than minimal risk to subjects, otherwise indicate each section as not applicable.

[Do not type here]

